6.0 Registry Visit Summaries

6.1 Screening/Baseline Visit #1

All potential subjects will be screened to ensure compliance to general inclusion and exclusion criteria. If subjects appear eligible to participate based on their medical history, they will be consented to participate in the registry. All consented subjects will undergo the following procedures:

- Obtain Informed Consent;
- Obtain Medical History and Current Medications;
- Administer a pregnancy test for all female subjects of child-bearing potential;
- Complete lymphedema evaluation;
- Complete the Clinical Intake Form (Appendix A);
- Obtain vital signs (if collected as part of standard of care);
- Obtain baseline ROM measurement (Appendix B);
- Obtain baseline swelling measurements (Appendix C);
- Have subject complete the EORTC C30 (Appendix D), EORTC H+N35 (Appendix E), and VAS (Appendix F);
- Instruct the subject on the methods to track compliance;
- Instruct subject on device prescription and training procedures at home or at the clinic; and
- Ensure a clinical research coversheet is submitted with the device order to Tactile Medical when ordering the Flexitouch system or Flexitouch Plus.

6.2 Device Training Visit #2 (Day 0)

All subjects will be instructed to conduct head and neck lymphedema treatment as prescribed by their treating clinician. Prior to using the Flexitouch system or Flexitouch Plus in-home, Tactile personnel will perform device training either in-home or at the clinic, per standard practice. The date of training (Day 0), which will

take place approximately 1-3 weeks after the device order is placed, will be used to determine the timing of the follow-up schedule.

6.3 Week 2 Phone Call Visit #3 (Day 14±3)

Approximately 14 days after the subject receives training and begins using the prescribed treatment, clinic personnel will call the subject to assess the following at Visit 3:

- Changes to medical history;
- Device-related adverse events (NOTE: Compare events to pre-existing conditions documented in Medical History to determine if the event is a new event, a worsening of a pre-existing event, or just a reoccurrence of a pre-existing event); and
- Any questions/concerns the subject has regarding device use and/or compliance.

6.4 Month 1 Clinic Visit #4 (Day 28±5)

Approximately 28 days after the subject begins using the prescribed treatment, he or she will return to the clinic and undergo the following procedures at Visit 4:

- Changes to medical history;
- Obtain vital signs (if collected as part of standard of care);
- Obtain ROM measurement (Appendix B);
- Obtain swelling measurements (Appendix C);
- Have subject complete the EORTC C30 (Appendix D), EORTC H+N35 (Appendix E), and VAS (Appendix F);
- Record device-related adverse events (NOTE: Compare events to pre-existing conditions documented in Medical History to determine if the event is a new event, a worsening of a pre-existing event, or just a reoccurrence of a pre-existing event); and
- Review treatment compliance with subject.

6.5 Month 2 Phone Call Visit #5 (Day 56±5)

Approximately 56 days after the subject begins using the prescribed treatment, clinic personnel will call the subject to assess the following at Visit 5:

- Changes to medical history;
- Device-related adverse events (NOTE: Compare events to pre-existing conditions documented in Medical History to determine if the event is a new event, a worsening of a pre-existing event, or just a reoccurrence of a pre-existing event); and
- Any questions/concerns the subject has regarding device use and/or compliance.

6.6 Month 3 Clinic Visit #6 (Day 84±5)

Approximately 84 days after the subject begins using the prescribed treatment, he or she will return to the clinic and undergo the following procedures at Visit 6:

- Changes to medical history;

- Obtain vital signs (if collected as part of standard of care);
- Obtain ROM measurement (Appendix B);
- Obtain swelling measurements (Appendix C);
- Have subject complete the EORTC C30 (Appendix D), EORTC H+N35 (Appendix E), and VAS (Appendix F);
- Record device-related adverse events (NOTE: Compare events to pre-existing conditions documented in Medical History to determine if the event is a new event, a worsening of a pre-existing event, or just a reoccurrence of a pre-existing event); and
- Review treatment compliance with subject.

6.7 Month 6 Clinic Visit #7 (Day 168±14)

Approximately 168 days after the subject begins using the prescribed treatment, or upon early termination of a subject (if possible), he or she will return to the clinic and undergo the following procedures at Visit 7:

- Changes to medical history;
- Obtain vital signs (if collected as part of standard of care);
- Complete lymphedema evaluation;
- Obtain ROM measurement (Appendix B);
- Obtain swelling measurements (Appendix C);
- Have subject complete the EORTC C30 (Appendix D), EORTC H+N35 (Appendix E), VAS (Appendix F), and Ease of Use and Treatment Satisfaction Survey (Appendix G);
- Record device-related adverse events (NOTE: Compare events to pre-existing conditions documented in Medical History to determine if the event is a new event, a worsening of a pre-existing event, or just a reoccurrence of a pre-existing event); and
- Review treatment compliance with subject.

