5.1.2 Secondary Endpoints

To evaluate quality of life (QOL), pain, swelling, ease of use, and treatment satisfaction after 168 days (approximately 6 months) of treatment with the Flexitouch system or Flexitouch Plus based upon:

- Change in the QOL (EORTC C30);
- Change in pain (VAS);
- Change in swelling (upper neck, lower neck, and ear to ear measurements); and
- Ease of use and treatment satisfaction (survey).

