6.8 Registry Exit

Once a subject completes all required visits, or chooses to withdraw from participation prior to Clinic Visit #7, ensure the following has been recorded:

- Date and reason for registry exit;
- Changes to medical history;
- Device-related adverse events (NOTE: Compare events to pre-existing conditions documented in Medical History to determine if the event is a new event, a worsening, of a pre-existing event or just a reoccurrence of a pre-existing event); and
- Treatment compliance.

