7.0 Registry Schedule of Activities

Procedures	Visit 1 (in clinic)	Visit 2 (in home or clinic)	Visit 3 (phone call)	Visit 4 (in clinic)	Visit 5 (phone call)	Visit 6 (in clinic)	Visit 7 (in clinic)
	Screen/ Baseline	Day 0	Week 2 (Day 14 ± 3 Days)	Month 1 (Day 28 ± 5 Days)	Month 2 (Day 56 ± 5 Days)	Month 3 (Day 84 ± 5 Days)	Month 6 (Day 168 ± 14 Days)
Informed Consent	X						
Device Training		X					
Pregnancy Test (if applicable)	X						
Medical History	X		X*	X*	X*	X*	X*
Vital Signs (if applicable)	X			X		X	X
Lymphedema Evaluation	X						X
Range of Motion (Neck, mouth, shoulders)	X			X		X	X
Assess Swelling	X			X		X	X
QOL (EORTC C30)	X			X		X	X
Symptoms (EORTC H+N35)	X			X		X	X
Assess Pain (VAS)	X			X		X	X
Ease of Use and Satisfaction Survey							X
Complications/ AEs/SAEs			X	X	X	X	X
Device Use Evaluation			X		X		
Compliance			X	X	X	X	X

* Change in medical history.

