9.0 Subject Withdrawal or Early Termination

Subject participation may be terminated prior to completing the registry for any of the following reasons:

- **Withdrawal of Consent**
Subjects may withdraw their consent to participate at any time. If a subject withdraws consent, previous information that has already been obtained will be available for analysis.
- **Lost to Follow-up**
A certified, return-receipt letter must be sent to the subject after 2 attempts to reach the subject by telephone have failed. The subject will be considered lost to follow-up if this communication is unsuccessful.
- **Adverse Event**
Subject experiences an adverse event that in the investigator's clinical judgement necessitates discontinuation of their participation in this registry.
- **Discretion of the Principal Investigator**
Subjects may be withdrawn at the investigator's discretion in the event of subject noncompliance, changes in the subject's health, or other reasons based on the investigator's clinical judgment.

When a subject withdraws prior to completing the registry, all effort should be made to complete Visit 7 prior to documenting the reason for withdrawal in the subject's medical record.

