15.0 Statistical Methods

For continuous variables, descriptive statistics will include the number of subjects (n), mean, standard deviation, median, inter-quartile range, minimum, and maximum, based upon subjects with reported data for the variable being analyzed.

Frequencies (numerator and denominator), percentages, and 95% confidence intervals will be displayed for categorical data. Percentages by categories will be based on the number of subjects with no missing (unreported) data for the specific variable being analyzed and the count of the patients for each individual level of the categorical variable (the level specific numerators). Percentages will add up to 100%, unless otherwise indicated.

There are no plans to impute missing data and there are no plans to explicitly report missing data (counts and/or percentages) in the tables for all variables as part of the planned study report content. Variations in the reported sample sizes within and/or between relevant tables can be used to ascertain insights into unreported data. In some cases, unreported data may be due to it not being clinically relevant to a particular patient or may represent expected data that was not collected. Selected analyses pertaining to unreported and/or missing data may be discussed and considered as future findings warrant.

The observational nature of the study suggests that the statistical focus will be on estimation and hypothesis generation and not hypothesis testing. Though p-values will be reported as apropos, point estimates, and 95% confidence intervals will be used to guide exploratory analyses for potentially clinically meaningful differences or changes to be discussed and evaluated.

Inter-group (e.g., bivariate) comparisons, when performed, will utilize chi-square, ANOVA, t-test, and appropriate non-parametric tests, unless otherwise specified.

Multivariable models (e.g., linear regression or logistic regression) may be used to assess the predictive relationships and control for possible confounding imbalances of selected multiple variables to specific outcome measures of interest.

Any formal null hypothesis-based statistical comparisons will be made using two sided tests at the $\alpha=0.05$ significance level unless specifically stated otherwise. All null hypotheses will be of no inter-group difference, all alternative hypotheses will be two-sided, unless specifically stated otherwise.

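### Subjects who leave without completing an exit Visit 7 fall out of the ease-of-use and satisfaction endpoint, and no count of them is planned

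*Combined protocol and SAP*

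**What the plan says.** Section 5.1.2 names "Ease of use and treatment satisfaction (survey" as a secondary endpoint, to be evaluated after 168 days of treatment. In the section 7.0 schedule, the row "Ease of Use and Satisfaction Survey" has a single mark, under Visit 7. The visit text agrees: section 6.7 includes "VAS (Appendix F), and Ease of Use and Treatment Satisfaction Survey (Appendix G", and sections 6.3 to 6.6 do not mention the survey.

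Visit 7 is not reserved for subjects who reach Day 168. Section 6.7 also applies it to early leavers: "or upon early termination of a subject (if possible), he or she will return to the clinic and undergo the following procedures at Visit 7". Section 9.0 adds that "all effort should be made to complete Visit 7 prior to documenting the reason for withdrawal in the subject's medical record".

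Section 6.8 sets the minimum record at registry exit. It starts with "Date and reason for registry exit" and goes on to medical history changes, device-related adverse events and compliance. The survey is not on that list. Section 9.0 also allows the investigator to withdraw a subject "in the event of subject noncompliance", and describes subjects who are lost to follow-up.

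For the analysis, section 15.0 states: "Percentages by categories will be based on the number of subjects with no missing (unreported) data for the specific variable being analyzed". Continuous variables are treated the same way. No imputation is planned, tables are not planned to carry missing counts, and any missing-data analysis is left to later judgement. Numerators and denominators are to be displayed.

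**The concern.** Among the listed endpoints, this is the only one with no measurement before Visit 7. Range of motion, swelling, the two EORTC questionnaires and the pain scale are all taken at Visits 1, 4, 6 and 7, so an early leaver may still contribute something on those. A subject who leaves and does not come back for the exit visit contributes nothing here.

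Non-response is also plausibly related to the answer. Someone who finds the garment hard to use or unhelpful is a natural candidate for stopping, for withdrawal as noncompliant, or for losing touch with the site. If so, a percentage computed on responders describes the more contented part of the registry. At stake is the reading of a named secondary endpoint, and a survey not obtained at exit cannot be recovered afterwards.

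**Working it through.** **Inputs.** From the documents: one survey time point (6.7, 7.0), a best-efforts exit visit (6.7, 9.0), no survey in the exit minimum (6.8), and responder-only denominators (15.0). The sample size is open, and no dropout rate, exit-visit completion rate or expected satisfaction rate is given. There is thus no plan figure to reproduce, and every rate below is an assumption.

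**Step 1: who is missing.** If a share d leaves early and a share c of those leavers completes the exit Visit 7, the share without a survey is m = d × (1 − c), plus any subject who attends Visit 7 but skips the form. For d = 20% and c = 50%, m = 0.20 × 0.50 = 10%.

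**Step 2: the range left open.** Take r = 90% satisfied among responders. Over all enrolled subjects the rate is lowest if every non-responder is dissatisfied, (1 − m) × r, and highest if every one is satisfied, (1 − m) × r + m.

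| No survey (m) | Lowest | Highest | Responder-only figure |
|---|---|---|---|
| 10% | 0.90 × 0.90 = 81% | 91% | 90% |
| 20% | 0.80 × 0.90 = 72% | 92% | 90% |
| 30% | 0.70 × 0.90 = 63% | 93% | 90% |
| 40% | 0.60 × 0.90 = 54% | 94% | 90% |

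Here m means no survey after any exit visit, so exit capture is already allowed for.

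**Step 3: direction.** If q is the satisfaction rate among non-responders, the responder-only figure exceeds the all-enrolled rate by m × (r − q). At m = 20%:

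- q = 0: 0.20 × 0.90 = 18 points too high
- q = 50%: 0.20 × 0.40 = 8 points too high
- q = 90%: no difference
- q = 100%: 0.20 × (−0.10) = 2 points too low

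**Step 4: how much exit capture helps.** This is a separate illustration, with 85% satisfied among completers, 30% among leavers, and d = 20%. The all-enrolled rate is 0.80 × 0.85 + 0.20 × 0.30 = 74.0%. The reported rate is (0.80 × 0.85 + 0.20 × c × 0.30) / (0.80 + 0.20 × c).

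| Leavers surveyed (c) | Reported | Excess over 74.0% |
|---|---|---|
| 0% | 85.0% | 11.0 points |
| 50% | 0.71 / 0.90 = 78.9% | 4.9 points |
| 80% | 0.728 / 0.96 = 75.8% | 1.8 points |
| 100% | 74.0% | 0 |

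With half the leavers surveyed, the excess runs from 2.6 points (d = 10%) to 8.3 points (d = 40%). If leavers are as satisfied as completers, it is zero throughout.

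**The case against.** A reader might infer that dissatisfied subjects who stop simply vanish from this endpoint. The documents do not support that. Sections 6.7 and 9.0 intend early leavers to have Visit 7, survey included, and step 4 shows that a well-executed exit visit removes most of the distortion. Stopping the device is also not the same as leaving the registry: withdrawal for noncompliance is at the investigator's discretion, and a non-user can still attend Visit 7. What stands is the gap for those who do not complete the exit visit.

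A reader might also infer that upward bias is certain. It is not. Subjects also leave because of adverse events or changes in health, nothing in the documents shows how satisfied leavers are, and the upper ends in step 2 lie above the responder figure.

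Nor would the report hide the problem completely. Section 15.0 displays numerators and denominators and points readers to differing sample sizes, and section 6.8 records the reason for exit. A reader could work out roughly how many surveys are absent. The tables would not, as planned, link the absences to reasons or show what they could do to the rate.

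Some usability information does exist earlier: the phone calls at Visits 3 and 5 (6.3, 6.5, 8.7) and the device observations, which include user preferences (8.10.3). These are not the Appendix G survey and do not replace it.

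Finally, responder-only reporting affects every endpoint, and the registry aims at estimation rather than testing. That supports treating this as a modest point. It does not remove the feature specific to this survey: a single best-efforts measurement that is absent from the exit minimum.

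**Conclusion.** The point holds in limited form. Subjects who leave without completing the exit Visit 7 are left out of a named secondary endpoint, and the plan neither counts them nor bounds their effect. Overstatement of satisfaction is likely, on the assumption that poor usability is one reason for leaving, but it is not established. Its size cannot be derived from the documents. Under the assumed 90% among responders, the all-enrolled rate could lie in 81–91% with 10% of surveys absent, widening to 54–94% with 40% absent.

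All enrolled subjects are a fair denominator, because section 5.2 counts a subject as enrolled only after device training, so each has been introduced to the device. One limit: the content of Appendix G is not shown, so whether it yields a percentage satisfied, and how well it suits completion by phone, should be confirmed. This is a cheap improvement, not a fundamental flaw.

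**What to change.** 1. **Section 6.8:** add the Appendix G survey to the exit list, and allow completion by phone when the clinic visit cannot be done.
2. **Section 15.0:** for this endpoint, report results with all enrolled subjects as denominator and no response as its own category, beside the responder-only figure and with the worst-to-best range from step 2.
3. **Tables:** show Day 168 and early-exit responses separately, since section 5.1.2 defines the endpoint after 168 days.
4. **Optional:** give the survey at Visit 4 as well, a clinic visit already held. Show those answers separately and do not carry them forward as the Day 168 result. Reporting the latest available answer would mix Day 28 impressions with the 168-day endpoint.

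The cost is a short call for some leavers and a few table rows, plus one extra form if the Visit 4 survey is adopted. The downside for the sponsor is a headline figure that may look less favourable. The exit change helps only subjects still to leave; the table change can be applied to everyone enrolled.

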6.8 Registry Exit

Once a subject completes all required visits, or chooses to withdraw from participation prior to Clinic Visit #7, ensure the following has been recorded:

- Date and reason for registry exit;
- Changes to medical history;
- Device-related adverse events (NOTE: Compare events to pre-existing conditions documented in Medical History to determine if the event is a new event, a worsening, of a pre-existing event or just a reoccurrence of a pre-existing event); and
- Treatment compliance.

7.0 Registry Schedule of Activities

Procedures	Visit 1 (in clinic)	Visit 2 (in home or clinic)	Visit 3 (phone call)	Visit 4 (in clinic)	Visit 5 (phone call)	Visit 6 (in clinic)	Visit 7 (in clinic)
	Screen/ Baseline	Day 0	Week 2 (Day 14 ± 3 Days)	Month 1 (Day 28 ± 5 Days)	Month 2 (Day 56 ± 5 Days)	Month 3 (Day 84 ± 5 Days)	Month 6 (Day 168 ± 14 Days)
Informed Consent	X						
Device Training		X					
Pregnancy Test (if applicable)	X						
Medical History	X		X*	X*	X*	X*	X*
Vital Signs (if applicable)	X			X		X	X
Lymphedema Evaluation	X						X
Range of Motion (Neck, mouth, shoulders)	X			X		X	X
Assess Swelling	X			X		X	X
QOL (EORTC C30)	X			X		X	X
Symptoms (EORTC H+N35)	X			X		X	X
Assess Pain (VAS)	X			X		X	X
Ease of Use and Satisfaction Survey							X
Complications/ AEs/SAEs			X	X	X	X	X
Device Use Evaluation			X		X		
Compliance			X	X	X	X	X

* Change in medical history.

8.0 Registry Procedures

8.1 Laboratory Testing Procedures

Women of childbearing potential will be tested for pregnancy according to the site specific procedures at the baseline visit. If the pregnancy test is positive, the subject will not be enrolled in the registry.

If the subject becomes pregnant at any time during the registry, the subject will be withdrawn from registry participation and followed at the Investigator's discretion.

8.2 Vital Signs & Lymphedema Evaluation

Research personnel will assess vital signs at each clinic visit (if collected as part of standard of care).

The clinical stage of lymphedema will be evaluated by a clinician at Baseline and Visit 7 using the following definitions:

- Stage 0: No visible edema but patient reports heaviness
- Stage 1a: Soft visible edema; no pitting, reversible
- Stage 1b: Soft pitting edema; reversible
- Stage 2: Firm pitting edema; not reversible; no tissue changes
- Stage 3: Irreversible; tissue changes

The evaluation will also document the presence or absence of issues with speech, edema, wounds, facial asymmetry, and skin changes.

8.3 Function Assessment

Cervical, mouth, and shoulder range of motion measurements will be taken at each in-clinic visit (Appendix B). The measurements will be completed by research personnel with documented training showing the individual was able to independently and accurately conduct the measurements on 2 occasions.

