5.0 Registry Design

This multi-center, prospective, observational, registry will follow patients with head and neck lymphedema who are using the Flexitouch system or Flexitouch Plus. Data collection will occur at Baseline and Days 14, 28, 56, 84, and 168.

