5.1 Endpoints

5.1.1 Primary Endpoints

To evaluate symptom and function improvement after 168 days (approximately 6 months) of treatment with the Flexitouch system or Flexitouch Plus based upon:

- Symptom survey (EORTC H+N35); and
- Range of motion measures (neck, mouth, and shoulder).

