8.4 Swelling Assessment

Swelling measurements will be taken at each in-clinic visit (Appendix C). The measurements will be completed by research personnel with documented training showing the individual was able to independently and accurately conduct the measurements on 2 occasions.

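### Every clinic visit lists ROM and swelling measurement before the subject's questionnaires, and earlier values are not kept from the measurer, so change from baseline may be biased in an unknown direction

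*Combined protocol and SAP*

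**What the plan says.** Section 5.0 describes the design: "This multi-center, prospective, observational, registry will follow patients with head and neck lymphedema who are using the Flexitouch system or Flexitouch Plus". It mentions no comparison group, and the protocol body says nothing about masking or independent assessment.

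The primary endpoint in Section 5.1.1 has a subject-reported part, "Symptom survey (EORTC H+N35); and", and a staff-measured part, "Range of motion measures (neck, mouth, and shoulder". Section 5.1.2 adds C30 quality of life, VAS pain and "Change in swelling (upper neck, lower neck, and ear to ear measurements); and", all as changes. It also lists ease of use and satisfaction, which the Section 7.0 schedule places at Visit 7 only.

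On who measures ROM, Section 8.3 states: "The measurements will be completed by research personnel with documented training showing the individual was able to independently and accurately conduct the measurements", with 2 occasions required. Section 8.4 repeats this for swelling: "The measurements will be completed by research personnel with documented training". Sections 8.5 and 8.6 say that the subject completes the H+N35, C30 and VAS, but not when within the visit.

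All four clinic visits list ROM, then swelling, then the forms. At Visit 7 (Section 6.7) the lymphedema evaluation also comes before this item: "Have subject complete the EORTC C30 (Appendix D), EORTC H+N35 (Appendix E), VAS (Appendix F), and Ease of Use and Treatment Satisfaction Survey". Section 14.6 has the site keep each subject's CRFs and source worksheets.

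**The concern.** Training addresses technique. It does not address what the measurer knows about the subject's earlier readings. Manual ROM and tape measurements leave room for judgement, and a person who has just seen the previous value may be influenced by it.

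The forms raise a parallel problem. A site that works down the visit list examines and measures the subject, may mention how the values have moved, and then asks for ratings of symptoms, quality of life and pain. Those ratings could then partly reflect the conversation.

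Both parts of the primary endpoint and three secondary change endpoints are exposed. In a controlled trial, a shift common to both arms would largely cancel in the comparison. Here the estimate is the within-subject change itself, so nothing removes it.

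**Working it through.** The plan has no figure to reproduce. Sample size is open, and no effect size, SD or power is given. The check is therefore a comparison of sections, followed by a short argument about bias.

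**Listed order within each clinic visit**

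| Visit (section) | Lymphedema evaluation | ROM, then swelling | C30, H+N35, VAS | Compliance review |
|---|---|---|---|---|
| Baseline (6.1) | before forms | before forms | after measurement | instruction only, after forms |
| Month 1 (6.4) | not done | before forms | after measurement | after forms |
| Month 3 (6.6) | not done | before forms | after measurement | after forms |
| Month 6 (6.7) | before forms | before forms | after measurement, with Appendix G | after forms |

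**What the body text provides as protection**

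- Measurer's technique: documented training on 2 occasions (8.3, 8.4).
- Measurer's access to earlier values: no rule. Earlier worksheets are held at the site (14.6).
- Order of forms and measurements: no rule beyond the lists above.
- When results may be discussed with the subject: no rule.
- Analysis: Section 15.0 does not discuss assessment bias.

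**How a shift enters the estimate**

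Let the recorded value be the true value plus a shift: s0 at baseline and s1 at follow-up. Then

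recorded change = true change + (s1 − s0).

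Split each shift into two parts.

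1. *Knowledge of earlier registry values or of measured change.* This is zero at baseline, because no earlier registry value exists. At follow-up it may be non-zero, and whatever it is passes in full into the mean change.
2. *General expectation, and the effect of being measured before answering.* This can be present at both visits. The subject is instructed on the device prescription at Visit 1, and the listed order is the same there. It cancels only so far as it is equal at the two visits.

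**Direction**

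The sign of s1 − s0 is not determined. A measurer who anchors on the previous value is drawn towards no change, which would shrink a real improvement. A measurer who expects benefit could be drawn the other way. A subject told of a good result may rate symptoms better; one told of a poor result may rate them worse.

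**Why open enrolment does not help**

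This step is illustrative only: b and n are assumed. Let b be the net bias in SDs of change, of either sign, with a true change of zero. The chance that a two-sided 95% interval excludes zero is approximately

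Φ(b√n − 1.96) + Φ(−b√n − 1.96).

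For b = 0.2 and n = 100: b√n = 2.0, so Φ(0.04) + Φ(−3.96) ≈ 0.516.

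| Assumed b | n = 30 | n = 100 | n = 400 |
|---|---|---|---|
| 0 | 5% | 5% | 5% |
| 0.1 | 8.5% | 17.0% | 51.6% |
| 0.2 | 19.5% | 51.6% | 97.9% |
| 0.3 | 37.6% | 85.1% | 100% |

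The table says nothing about how large b is in this registry. It shows only that, if b is not zero, more enrolment narrows the interval around a displaced value.

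**The case against.** The strongest reply is that much of the mechanism is inferred.

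- The visit bullets are not presented as a required sequence.
- No section says that staff look up earlier values or tell subjects their results.
- Appendix B (ROM) and Appendix C (swelling) appear by title only and may contain recording instructions.
- Section 15.0 describes the work as estimation and hypothesis generation, so this is good practice rather than the correction of an error.
- Forms first would not remove expectation, since everyone knows the device is in use.

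Most of this stands, and it limits the claim. A reader might infer that the influence runs only towards improvement. The documents do not support that, because anchoring on an earlier value pulls towards no change. A reader might also infer that expectation acts at follow-up only. That holds for knowledge of earlier values and of change, but not for expectation in general, which exists at baseline too. Nor is every secondary endpoint affected through change from baseline: ease of use and satisfaction has no baseline.

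Two parts of the reply do not dispose of the point. An exploratory aim is no protection, because Section 15.0 relies on point estimates and 95% intervals to identify meaningful changes, and bias displaces both. Silence on order is no protection either: a site that simply follows the lists collects the forms after examination and measurement.

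**Conclusion.** The point holds in a limited form. In the protocol body, measurement precedes the subject's forms in every clinic visit list, and nothing keeps earlier values from the measurer or delays discussion of results. With one cohort and no comparator, this may bias change from baseline in ROM, swelling, H+N35, C30 and VAS. Neither direction nor size can be derived from the documents, and no numerical magnitude should be attached.

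The conclusion assumes that at least some sites work roughly in the listed order or have earlier worksheets to hand, and that Appendices B and C do not already restrict access. If they do restrict it, the measurement half falls away and the ordering of the forms remains. The change is worth making because it protects both parts of the primary endpoint at almost no cost.

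**What to change.** - In Sections 6.1, 6.4, 6.6 and 6.7, have the subject complete the C30, H+N35 and VAS (and Appendix G at Visit 7) before the lymphedema evaluation, where one is done, and before ROM and swelling measurement. State that this order is required.
- In Sections 8.3 and 8.4, require values to be recorded on a fresh worksheet with earlier values out of view. Results should be discussed with the subject only after all forms are complete.
- Leave the compliance review where it is; it is already listed after the forms.

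The cost is four reordered lists and a sentence or so in each of 8.3 and 8.4. No extra assessor or visit is needed, and the planned analysis is unchanged. Sites must keep earlier worksheets out of sight during measurement. Because enrolment is open, record the date on which each site adopts the change, so that data collected before and after it can be told apart. This includes subjects whose baseline falls before that date and whose Visit 7 falls after it.
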